6.1.1 Selection of endpoints

A key pathophysiological element of diastolic dysfunction and heart failure with preserved ejection fraction is the inability to increase cardiac output without concomitant excessive increase in LV filling pressure during physical strain. Thus the ratio between LV filling pressure to cardiac output will be abnormally increased during exercise. In many patients filling pressure will be normal or mildly elevated at rest where cardiac output will be normal. Thus resting assessment will often be misleadingly normal in these patients where as evaluation during exercise will uncover the pathophysiology (5,6). By combining filling pressure and cardiac output it will be possible indirectly to assess changes in the pressure volume relationship of the LV which not would be the case if either PCWP or cardiac index alone were chosen.

Cardiac MRI with late gadolinium enhancement is a useful tool for detection of myocardial fibrosis, based on differences in the volume of distribution of gadolinium (13). Although the method is especially well suited to detect the presence of fibrosis in the myocardium in ischemic cardiomyopathy, it may also detect myocardial fibrosis in a wide variety of non-ischemic cardiomyopathies. Modification of myocardial fibrosis will provide an important pathophysiological link between assessment of central hemodynamics during exercise and effects of ARNi. In addition cMRI provides detailed information on cardiac structure thus it will provide very precise data on LV remodeling (LV volumes and LV mass) and LA remodeling. Thus provide important explanatory data.

ST2 is a member of the interleukin 1 receptor family. The ST2 gene is highly expressed by cardiomyocytes and fibroblasts when strained in this setting ST2L becomes receptive for interleukin-33 which has antihypertrophic and antifibrotic effects (14). Thus ST2 concentration reflects cardiac

remodeling and myocardial fibrosis. After AMI ST2 has been demonstrated to predict prognosis (15) and be associated with presence of heart failure. Differences in ST2 concentrations between groups will provide insights into the mechanisms of the potential effect of ARNi.

6.1.2 Selection of comparator

Current guidelines recommend treatment with an angiotensin II receptor blocker or an angiotensin converting enzyme inhibitor in all patients with signs or symptoms of heart failure and/or evidence of LV dysfunction in the absence of hypotension, hypovolaemia, or renal failure with a class I indication (17,18). Thus the patients selected in the present study do not have a class I indication for blockade of the renin angiotensin system. Thus the comparator will be placebo which also will provide the strongest insight into the effect of ARNi on myocardial structure and function.

6.1.3 Sample size

Based on previous data it is expected that PCWP will increase to 32 ± 8 mmHg and cardiac index to 7.4 ± 1.4 l/min/m², with a PCWP/CI ratio of 4.49 ± 1.4 (19).

To detect a decrease of 20% in primary endpoint with alpha of 0.05 and beta 0.8, a total of 90 patients are required, to allow 10% dropout rate 100 patients are expected to be enrolled.

| Difference in PCWP/CI ratio | Standardized difference | N (Total) $\alpha=0.05/\beta=0.8$ | N (Total) $\alpha=0.05/\beta=0.9$ |
|-----------------------------|-------------------------|--------------------------------------|--------------------------------------|
| 10% (0.449) | 0.299 | 320 | 450 |
| 15% (0.674) | 0.449 | 150 | 200 |
| 20% (0.898) | 0.598 | 90 | 110 |
| 25% (1.12) | 0.748 | 70 | 100 |

7 Timelines and Study duration:

Start date: June 2018

Approval from relevant authorities: Medio august 2018

Inclusion start: 1/9 2018

Last patient last visit: July 2020

End date: July 2020

Clinical study report date: August 2020

Publication date: September 2020 – May 2021

8 Population:

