| Study Population | A total of 100 male or nonpregnant females aged ≥ 50 years with a recent documented AMI, diastolic dysfunction, and LVEF $\geq 45\%$ on echocardiography performed within 72 hours of the AMI will be enrolled at selected invasive centers in Denmark. | | | | | | | | | | | | | | | | | | | | |
| Sample Size Considerations | 
Based on previous data it is expected that PCWP will increase to 32 ± 8 mmHg and cardiac index to 7.4 ± 1.4 l/min/m², with a PCWP/CI ratio of 4.49 ± 1.4. To detect a decrease of 20% in primary endpoint with alpha of 0.05 and beta 0.8, a total of 90 patients are required, to allow 10% dropout rate 100 patients are expected to be enrolled.
 
  
 Difference in PCWP/CI ratio	Standardized difference	N (Total) $\alpha=0.05/\beta=0.8$	N (Total) $\alpha=0.05/\beta=0.9$	
   
 10% (0.449)	0.299	320	450	
 
 15% (0.674)	0.449	150	200	
 
 20% (0.898)	0.598	90	110	
 
 25% (1.12)	0.748	70	100	
  
 | Difference in PCWP/CI ratio | Standardized difference | N (Total) $\alpha=0.05/\beta=0.8$ | N (Total) $\alpha=0.05/\beta=0.9$ | 10% (0.449) | 0.299 | 320 | 450 | 15% (0.674) | 0.449 | 150 | 200 | 20% (0.898) | 0.598 | 90 | 110 | 25% (1.12) | 0.748 | 70 | 100 |
| Difference in PCWP/CI ratio | Standardized difference | N (Total) $\alpha=0.05/\beta=0.8$ | N (Total) $\alpha=0.05/\beta=0.9$ | | | | | | | | | | | | | | | | | | |
| 10% (0.449) | 0.299 | 320 | 450 | | | | | | | | | | | | | | | | | | |
| 15% (0.674) | 0.449 | 150 | 200 | | | | | | | | | | | | | | | | | | |
| 20% (0.898) | 0.598 | 90 | 110 | | | | | | | | | | | | | | | | | | |
| 25% (1.12) | 0.748 | 70 | 100 | | | | | | | | | | | | | | | | | | |
| Inclusion Criteria | 
 1. Documented ST segment elevation or non ST- myocardial infarction according to current guidelines 2. Complete revascularization 3. Age ≥ 50 years 4. LVEF $\geq 45\%$ on echocardiography performed within 72 hours of the MI. 5. Diastolic dysfunction defined as: Ratio of early diastolic peak mitral inflow velocity (E) to early mitral annulus diastolic velocity (e') ratio > 8 and at least moderate LA dilatation (LA volume index > 34 mL/m²). 6. Signed informed consent | | | | | | | | | | | | | | | | | | | | |

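### The sample-size text gives the PCWP/CI ratio an SD of 1.4, but the table's standardised differences and the 90 patients required rest on an unstated SD of 1.5; the enrolment of 100 holds under either

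*Protocol*

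**What the plan says.** Protocol section 6.1.3 (Sample size) takes its planning values from an earlier study. For the two components, "it is expected that PCWP will increase to 32 ± 8 mmHg and cardiac index to 7.4 ± 1.4" (the second in l/min/m²). For the ratio itself, the section cites the same study and plans "with a PCWP/CI ratio of 4.49 ± 1.4 (19"). The synopsis, under Sample Size Considerations, repeats the ratio: "with a PCWP/CI ratio of 4.49 ± 1.4". For a 20% decrease the text concludes "with alpha of 0.05 and beta 0.8, a total of 90 patients are required". Its allowance for loss comes next: "to allow 10% dropout rate 100 patients are expected to be enrolled".

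The table that follows lists, for decreases of 10%, 15%, 20% and 25%, the absolute difference, the standardised difference, and the total N in two columns headed β=0.8 and β=0.9. The design row reads "20% (0.898) | 0.598 | 90 | 110". The same table appears in the synopsis.

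Section 9.2 rests the 100 randomised patients, 50 per arm, on this calculation. The SAP has no sample-size section, so this is the only justification on record.

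**The concern.** A standardised difference is the absolute difference divided by the SD. With the stated SD of 1.4, the design row should show 0.898 / 1.4 = 0.641, not 0.598. If the text and table use different SDs, the stated N cannot follow from the stated inputs, and a reader cannot tell which SD the trial was planned on.

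This bears on how much missing data the trial can absorb. The primary endpoint needs a repeat invasive exercise test at 26 weeks, so losing some evaluable patients is a practical possibility. The two SDs give different answers about how many can be lost before power falls below 80%.

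**Working it through.** **Inputs.** Mean ratio 4.49 and SD 1.4 (6.1.3 and synopsis); 20% decrease = 0.20 × 4.49 = 0.898; alpha 0.05; power 80% (the text's beta 0.8, read as power); allocation 1:1 (section 6). Section 6.1.3 names no test or sidedness. A two-sided two-sample t-test is assumed; the two-sided 95% confidence interval in section 15.2 supports the sidedness.

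**Step 1. The SD implied by the table** (SD = difference / standardised difference).

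| Decrease | Difference | Printed standardised difference | Implied SD | Standardised difference at SD 1.4 |
|---|---|---|---|---|
| 10% | 0.449 | 0.299 | 1.502 | 0.321 |
| 15% | 0.674 | 0.449 | 1.501 | 0.481 |
| 20% | 0.898 | 0.598 | 1.502 | 0.641 |
| 25% | 1.12 | 0.748 | 1.497 | 0.802 |

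(The last cell uses the unrounded difference, 0.25 × 4.49 = 1.1225.) All four rows give 1.5, so this is not a slip in one cell.

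**Step 2. Reproducing the plan's 90.** The normal approximation is N(total) = 4 × (1.960 + 0.842)² × (SD / 0.898)², rounded up to equal arms. The t-based figure uses the noncentral t distribution.

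- SD 1.5: 88 by the normal approximation, 90 by the t-test. The plan's 90 is reproduced.
- SD 1.4: 78 by the normal approximation, 80 by the t-test. The plan's 90 is not reproduced.
- Other settings at SD 1.4 (normal approximation unless stated): one-sided alpha gives 62 (80% power) or 84 (90% power); two-sided with 90% power gives 104, or 106 by the t-test. None gives 90.
- Rounding: an SD printed as 1.4 is below 1.45. At 1.45 the t-test needs 84 and the standardised difference is 0.898 / 1.45 = 0.619, so rounding does not explain 90 or 0.598.

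**Step 3. Dropout.** 90 / 0.9 = 100, which is correct. Starting from SD 1.4, 80 / 0.9 = 88.9, or 89, so 100 is also enough there. The 89 is close to 90, but the plan presents 90 as the number before dropout and inflates it to 100.

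**Step 4. Power for a 20% decrease, by number evaluable (t-test).**

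| Evaluable | SD 1.4 | SD 1.5 |
|---|---|---|
| 80 | 80.9% | 75.3% |
| 88 | 84.5% | 79.3% |
| 90 | 85.3% | 80.1% (printed 0.598) or 80.2% (0.898 / 1.5) |

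At SD 1.4, 78 patients give 79.9%, just short. So of 100 enrolled, 20 can be lost at SD 1.4 and 10 at SD 1.5. With 90 evaluable patients, the smallest decrease detectable with 80% power is 18.6% at SD 1.4 and about 20% at SD 1.5.

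**Step 5. The other N cells, at the table's own standardised differences.**

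| Decrease | Printed N (80% / 90%) | Power at printed N | N needed (80% / 90%) |
|---|---|---|---|
| 10% | 320 / 450 | 76.0% / 88.6% | 354 / 474 |
| 15% | 150 / 200 | 78.0% / 88.5% | 158 / 212 |
| 20% | 90 / 110 | 80.1% / 87.5% | 90 / 120 |
| 25% | 70 / 100 | 87.0% / 95.9% | 60 / 78 |

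The largest departures are the 320 in "10% (0.449) | 0.299 | 320 | 450", which is 4 power points short, and both N in "25% (1.12) | 0.748 | 70 | 100", which are well above what is needed. The cells 110, 150, 200 and 450 are 1.4 to 2.5 points short. At SD 1.4 the required N would be 308 / 412, 138 / 184, 80 / 106 and 52 / 68. Apart from the 90, the printed N follow from neither SD.

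**Step 6. Can the documents settle which SD is right?** The components in the same sentence (PCWP 32 ± 8, CI 7.4 ± 1.4) were simulated with 4 million draws, assuming no correlation. The ratio came out at 4.50 ± 1.51 if both are normal and 4.48 ± 1.42 if both are lognormal. Assumed correlations from -0.1 to +0.1 widen the SD range to 1.34 to 1.59. The documents give neither distribution nor correlation, so both 1.4 and 1.5 remain possible.

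**The case against.** The best reply is that nothing turns on the discrepancy. The error is conservative: if the SD is really 1.4, the trial has more power than planned. The text already gives a loss allowance of 10%, and that is the stricter of the two, so anyone relying on it is safe. The planned analysis is ANCOVA (or, in the SAP, possibly a mixed model) with baseline as an optional covariate. Adjusting for baseline would reduce the N needed by a factor of 1 − r². For an assumed correlation r of 0.3 to 0.5 (the documents give none), 90 falls to 90 × 0.91 = 82 or 90 × 0.75 = 68. The printed N are all multiples of ten and look approximate, and only the 90 sets the sample size. Reading beta as power is obvious.

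Much of this stands. Enrolment is unaffected, the loss margins above hold only for an unadjusted t-test, and the cells outside the design row have no operational role. The reply does not remove the contradiction, however: the stated SD and the stated N do not belong together. Nor does approximate rounding explain the N column, where the errors run in both directions (320 too low; 70 and 100 too high).

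**Conclusion.** The point holds, with minor consequence. The text's SD of 1.4 requires 80 evaluable patients, while the stated 90 and every standardised difference come from an SD of 1.5 that appears nowhere. The trial is not underpowered on its own inputs: 90 evaluable patients give between 80.1% and 85.3% power for a 20% decrease, and 100 enrolled is sufficient under both SDs. What is left open is whether the trial was planned for about 80% or about 85% power at 90 patients, and whether the margin for loss is 10 or 20 patients.

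These figures assume a two-sided, unadjusted two-sample t-test at 0.05 with equal arms. The documents do not show which SD is correct.

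**What to change.** In section 6.1.3 and the synopsis, report the cited SD as its source gives it, state the planning SD separately with the reason for it, and name the test and its sidedness. Relabel beta 0.8 and 0.9 as power.

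- **If the planning SD is 1.5:** keep 90 and 100. Correct the other cells to 354 / 474 (10%), 158 / 212 (15%), 120 (20%, 90% power) and 60 / 78 (25%), or delete the rows that are not used.
- **If the planning SD is 1.4:** use standardised differences 0.321, 0.481, 0.641 and 0.802 with N of 308 / 412, 138 / 184, 80 / 106 and 52 / 68, and state that 90 evaluable patients give about 85% power.

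Enrolment stays at 100 in both cases. The cost is a text and table correction in two places, with no change to design, endpoint or analysis. If the protocol can no longer be amended, one sentence on the planning SD in the SAP or the trial report is enough.

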8.1 Key inclusion criteria

1. Documented ST segment elevation or non ST- myocardial infarction according to current guidelines (20).
2. Complete revascularization.
3. Age ≥ 50 years
4. LVEF $\geq 45\%$ on echocardiography performed within 72 hours of the MI.
5. Diastolic dysfunction defined as: Ratio of early diastolic peak mitral inflow velocity (E) to early mitral annulus diastolic velocity (e') ratio > 8 and LA dilatation (LA volume index > 34 mL/m²).
6. Signed informed consent

8.2 Key exclusion criteria

1. Intolerance towards study medication
2. Permanent atrial fibrillation,
3. Known history of cardiomyopathy,
4. More than mild valvular heart disease,
5. Severe obstructive or restrictive pulmonary disease,
6. Inability to perform exercise testing,
7. Inadequate acoustic windows on echocardiography,
8. Ongoing treatment with an angiotensin converting enzyme inhibitor at randomization.
9. Class I indication for an angiotensin converting enzyme inhibitor
10. Symptomatic hypotension, a systolic blood pressure of less than 100 mm Hg at screening
11. An estimated glomerular filtration rate (eGFR) below 30 ml per minute per 1.73 m² of body-surface area at any time,
12. A serum potassium level of more than 5.2 mmol per liter at screening,
13. A history of hereditary or idiopathic angioedema or unacceptable side effects during receipt of angiotensin converting enzyme inhibitor or angiotensin receptor blocker
14. Inability to provide informed consent
15. Concomitant use of drugs containing aliskiren in patients with diabetes mellitus.
16. Severe reduced liver function, biliary cirrhosis or cholestasis (Child-Pugh class C)
17. Pregnant or nursing(lactating) women(see section 8.2.1 for details)
18. Fertile women unless they are using a highly effective method of contraception(see section 8.2.2 for details)

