3.2 LCZ696

LCZ696 is a combination drug consisting of two antihypertensives, valsartan and sacubitril. Valsartan acts by blocking the angiotensin II receptor type 1 and thereby causes vasodilation and increases excretion of sodium and water via the kidneys by attenuating aldosterone production. Sacubitril is a prodrug that is activated to an active metabolite (LBQ657) that acts by inhibiting the enzyme neprilysin (8). Neprilysin is responsible for the degradation of natriuretic peptides released from the LV and left atrium in response to increased wall stress and myocyte stretch and act by attenuating the deleterious effects of volume and pressure overload on the heart, a protective mechanism that have been suggested to be deficient in early stage of heart failure with preserved LVEF (9). Augmentation of these mechanisms likely at least partly explain the beneficial effect on outcome of ARNi in heart failure with reduced LVEF that recently was found in the PARADIGM-HF trial, where angiotensin receptor – neprilysin inhibition (ARNi) compared with enalapril treatment was associated with a risk reduction of 20% of composite primary endpoint death and hospitalization for heart failure (10). In patients with heart failure and preserved ejection fraction ARNi has been demonstrated to have a beneficial effects on natriuretic peptides and left atrial remodeling in a clinical Phase II trial (11). Furthermore, recent experimental data also suggest ARNi attenuated cardiac remodeling and dysfunction after experimental AMI in rodents and importantly inhibit cardiac fibrosis in experimental AMI, as well as in vitro beyond that achieved by stand-alone angiotensin receptor blockade (12).

Thus in theory LCZ696 may possess several beneficial properties that may improve hemodynamics and cardiac remodeling in patients with diastolic dysfunction after AMI.

4 Hypothesis:

LCZ696 compared with placebo will improve central hemodynamics (reduce pulmonary capillary wedge pressure (PCWP)), and increase cardiac index (CI) during exercise in patients with diastolic dysfunction after AMI. A beneficial effect that is attributed to improved cardiac remodeling (attenuation of cardiac fibrosis).

5 Objectives:

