^a Unblinded measurements: Hemoglobin, platelet count, white blood cell count(WBC), WBC differential, alanine aminotransferase (ALT), albumin, total bilirubin, alkaline phosphatase, blood urea nitrogen, calcium, creatinine, potassium, sodium, glucose, lipid profile(total cholesterol, LDL, HDL and triglycerides). Additional blood samples are drawn and stored for later analysis of NT-proBNP, MR-pro-ANP, ST2 and possible future biomarkers.

Patients who meet the study inclusions and none of the exclusion criteria will after signing an Ethics Committee approved Informed Consent Form, will undergo conventional spirometry, blood testing, comprehensive resting Doppler echocardiography, cardiac MRI with late enhancement imaging, resting right heart catheterization, and symptom-limited supine cycle exercise test with simultaneous echocardiography and right heart catheterization will be performed before randomization.

After randomization patients will be started on LCZ696 49/51 mg twice daily or matching placebo twice daily titrated to their final doses of LCZ696 97/103 mg twice daily or matching placebo twice daily over a period of 2–4 weeks. Succeeding up titration to final dose a visit is planned after two weeks (visit 2) to assess tolerability. In case of clinical concern regarding tolerability additional follow up is left at discretion of the investigator.

Background therapy will be decided at the discretion of treating physicians. The double-blind design will continued for 26 weeks. After 26 weeks treatment cardiac MRI, echocardiography, right heart catheterization and exercise test will be repeated.

Patients will in addition to the above mentioned be followed in the “Prevention and aftercare out-patient clinic” as per standard care following AMI.

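### Exclusion criterion 8 bars patients on an ACE inhibitor but not patients on an angiotensin receptor blocker (ARB), although LCZ696 itself contains an ARB

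*Protocol*

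**What the plan says.** Criterion 8 in Protocol section 8.2, worded identically in the synopsis, excludes "Ongoing treatment with an angiotensin converting enzyme inhibitor at randomization". Criterion 9 excludes a "Class I indication for an angiotensin converting enzyme inhibitor". ARBs are named only in criterion 13, which concerns past "unacceptable side effects during receipt of angiotensin converting enzyme inhibitor or angiotensin receptor blocker". Criterion 15 bars "Concomitant use of drugs containing aliskiren in patients with diabetes mellitus".

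Section 3.2 describes the study drug: "LCZ696 is a combination drug consisting of two antihypertensives, valsartan and sacubitril". The same section says that valsartan blocks the angiotensin II type 1 receptor.

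Section 6.1.2 treats the two drug classes as alternatives ("Current guidelines recommend treatment with an angiotensin II receptor blocker or an angiotensin converting enzyme inhibitor", for patients with heart failure or LV dysfunction). It argues that trial patients have no class I indication for blocking this system, and adds that placebo gives the "strongest insight into the effect of ARNi on myocardial structure and function".

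For the period after randomisation, section 11 says: "Background therapy will be decided at the discretion of treating physicians". The SAP does not mention concomitant ACE inhibitors or ARBs.

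**The concern.** The list excludes current use of the drug class that is not in LCZ696 and leaves out the class that is. A patient taking an ARB for a reason other than a class I indication can therefore be randomised with the rules followed to the letter.

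Two things are at stake. The first is safety: on LCZ696 this patient has double exposure to the ARB class, in a trial whose section 12.2 names symptomatic hypotension as a risk of the study drug. Renal function and potassium are the other natural worries. The second is interpretation: on placebo this patient already receives the mechanism of one of the two components of LCZ696, so the contrast with placebo may shrink. Allocation is randomised and blinded, so the worry is attenuation of the effect, not confounding.

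**Working it through.** **Step 1. Does any criterion close the gap?** Take a patient who has a recent infarction, has taken an ARB for hypertension without trouble, and has no class I indication for an ACE inhibitor.

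| Criterion (section 8.2) | What it covers | Stops this patient? |
|---|---|---|
| 1 | Intolerance of study medication | No, the ARB is tolerated |
| 8 | Current ACE inhibitor | No, the drug is an ARB |
| 9 | Class I indication for an ACE inhibitor | No, there is none |
| 10–12 | Low blood pressure, low eGFR, high potassium | Only if a limit is crossed |
| 13 | Past ACE-inhibitor or ARB side effects, or angioedema | No |
| 15 | Aliskiren in diabetes | No |

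The list is headed as key criteria, but neither document gives a fuller one. The patient is eligible.

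**Step 2. Does the rationale explain the omission?** Section 6.1.2 argues from the absence of a class I indication. That is a statement about indication, not about what the patient takes. It gives no reason for treating a current ARB differently from a current ACE inhibitor.

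**Step 3. How large could the dilution be?** The plan gives no figure for this, so the inputs are partly assumed.

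- From section 6.1.3: planned difference D = 0.898 (20% of 4.49), 90 evaluable patients (45 per arm), two-sided alpha 0.05. The printed SD is 1.4. The table's standardised difference of 0.598 implies 0.898/0.598 ≈ 1.5, so both are shown.
- Assumed: a share f of patients enters on an ARB, equally in both arms. The ARB gives a share e of the LCZ696 effect to placebo patients and adds nothing on top of LCZ696.

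The plan's own sample size first: with a standardised difference of 0.598 and 80% power, a two-sample t-test needs about 90 patients in total, as stated, and 90/(1 − 0.10) = 100.

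Among ARB users the treatment difference is D(1 − e). Averaged over all patients it is

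D(1 − f) + D·f·(1 − e) = D(1 − f·e).

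| f | e | Difference | Power, SD 1.5 | Power, SD 1.4 |
|---|---|---|---|---|
| 0 | – | 0.898 | 80.2% | 85.3% |
| 5% | 25% | 0.898 × 0.9875 = 0.887 | 79.2% | 84.4% |
| 10% | 50% | 0.898 × 0.95 = 0.853 | 76.1% | 81.6% |

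The loss is about 1 point in the second row and about 4 points in the third. In the third row, 10 of 100 patients enter on an ARB and about 5 of them receive a double ARB. If the ARB adds equally in both arms, or nobody takes one, the loss is nil.

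**The case against.** The strongest reply is that the plan already contains safeguards. Criteria 10–12 exclude systolic pressure below 100 mm Hg, eGFR below 30 and potassium above 5.2 mmol/l. Section 11 schedules vital signs, laboratory tests (including creatinine and potassium) and concomitant medication at all four visits. It also plans a tolerability visit two weeks after up-titration. Section 11.1 stops study drug when eGFR falls below 30, when hypotension persists despite action, or when the investigator judges that treatment harms the patient. Section 11.1.1 has concomitant drugs reviewed and reduced before the study dose is lowered. All of this stands. It limits the harm, but it acts after exposure has begun or only at the extremes, and it does not make the exposure intended.

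A second reply is that leaving background therapy to treating physicians is an ordinary add-on design, and that the narrow aliskiren exclusion does not show an intention to bar every drug acting on this system. That is fair. The point rests instead on the asymmetry in criterion 8: an ACE inhibitor is barred, while the class inside the study drug is not.

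A third reply is that the power figures rest wholly on assumptions. That is correct. Section 3.2 also credits neprilysin inhibition with effects beyond an ARB alone, so a contrast would survive in ARB users. The figures are unadjusted too. If baseline were used as a covariate with an assumed correlation of 0.6, the 10%/50% case at SD 1.5 would lose about 2.4 points (93.9% to 91.5%).

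A reader might go further and infer that section 11 should forbid later ACE-inhibitor or ARB use and require study drug to be stopped. That does not follow. Later starters who stop LCZ696 but stay in the intention-to-treat analysis leave a difference of D(1 − g), where g is their share. With g = 10% this is 0.808 and power is 71.5%, against 76.1% if they continue (SD 1.5, e = 50%). That is a separate trade-off, and the documents give no rates with which to settle it.

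**Conclusion.** The gap is real. As written, criterion 8 admits a patient on a tolerated ARB, and neither another criterion nor the stated rationale accounts for it. The consequence is possible double ARB-class exposure or an ARB-treated placebo patient. The added risk is avoidable but partly mitigated, and the dilution may be small or nil.

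The size cannot be fixed from the documents, because they report no ARB use. The loss of 1 to 4 points shown above is an illustration under assumed shares and effects, not an estimate.

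Three stronger readings are not supported. The documents do not show that any patient received a double ARB or was harmed. They do not show that valsartan itself is duplicated, since a background ARB repeats the class and is the same drug only if it happens to be valsartan. They do not show a biased comparison, since randomisation and blinding leave attenuation as the concern.

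Priority is low. The last visit was planned for July 2020 (section 7) and the SAP is dated 07022024, so enrolment is very probably closed.

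**What to change.** If enrolment is open, insert *or angiotensin receptor blocker* directly after the ACE-inhibitor wording in criterion 8, in section 8.2 and in the synopsis, so that both classes are barred at randomisation. The cost is one phrase in two places and a slightly smaller eligible pool. No change to section 11 is proposed.

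If enrolment is closed, that edit is moot. What remains is an optional table of ACE-inhibitor and ARB use by arm and visit. It needs no new data, because concomitant medication is scheduled for recording at all four visits, and it would show whether the gap mattered in practice.
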